#### **5.8.3. Analysis of Vital Signs**

Vital signs - temperature, blood pressure, heart rate (semi-recumbent and standing), orthostatic blood pressure/heart rate, and respiration rate- are to be summarized by baseline and change from baseline to each scheduled assessment time with descriptive statistics by treatment group and combined REGN5069 for the SAF, for treatment period and follow-up period.

PCSV summary including orthostatic hypotension is to be constructed for treatment period, period and overall during the study, as well as presented in a listing.

#### **5.8.4. Analysis of 12-Lead ECG**

ECG parameters (Ventricular Rate, PR/PQ, QRS, QT and QTcF intervals) are to be summarized by baseline and change from baseline to each scheduled and collected assessment time. PCSV summary of ECG parameters is to be provided for treatment period, Follow-up period, and overall, for the SAF.

ECG status (ie, normal, abnormal) is to be reported. Shift tables are to be provided to present the post-baseline status according to the baseline status (normal or missing / abnormal) by treatment. Listings are to be provided with flags indicating the abnormal values.

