#### **4.5.1. Adverse Events and Serious Adverse Events**

Adverse event information is to be collected until the patient’s last study visit. Serious adverse event information is to be collected until the event is considered chronic and/or stable and/or resolved.

Adverse events (AE) and Serious Adverse Events (SAE) are collected from the time of informed consent signature and then at each visit until the end of follow-up visit (week 36) for AEs and until end of study visit (week 52) for SAEs. All AEs are to be coded to a “Preferred Term (PT)” and associated primary “System Organ Class (SOC)” according to the MedDRA® (the latest current available version).

An AE is any untoward medical occurrence in a patient administered a study drug which may or may not have a causal relationship with the study drug. Therefore, an AE is any unfavorable and unintended sign (including abnormal laboratory finding), symptom, or disease which is temporally associated with the use of a study drug, whether or not considered related to the study drug. An AE also includes any worsening (ie, any clinically significant change in frequency and/or intensity) of a pre-existing condition that is temporally associated with the use of the study drug. Laboratory results, vital signs, or ECG abnormalities are to be recorded as AEs if they are medically relevant: symptomatic, requiring corrective therapy, leading to treatment discontinuation and/or fulfilling a seriousness criterion.

An SAE is an AE that is classified as serious according to the criteria specified in the protocol. SAEs with an onset within 30 days of the end of the follow-up period or within 226 days of last study drug administration if the patient early terminated from the study is to be reported to the sponsor. SAEs with an onset day greater than 30 days from the end of the follow-up period/early termination visit: only fatal SAEs and those deemed by the investigator to be drug-related SAEs are to be reported to the sponsor. SAEs reported by the patient at the end-of-study phone call and deemed by the investigator to be drug-related are to be reported to the sponsor.

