#### 4.5.9. 12-Lead Electrocardiography (ECG)

A standard 12-lead ECG is to be performed according to the Schedule of Events in Table 3 with the patient in the semi-recumbent position for approximately 10 minutes and prior to blood samples being drawn. Heart rate is recorded from the ventricular rate and the PR/PQ, QRS, and QT, QTcF intervals, and ECG status (normal, abnormal not clinical significant or abnormal clinical significant) is also recorded.

QTcF is defined as follows:

$$\text{QTcF (ms)} = \text{QT/RR}^{1/3},$$

where QT is the uncorrected QT interval measured in ms, and RR is 60/HR with HR being the heart rate in beats per minute.

Potentially clinically significant values (PCSV) ranges are to be applied to the ECG parameter values as applicable (see Appendix 11.2 for PCSV definitions).

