#### **5.8.7. Neurological Exam**

New-onset clinically significant abnormal neurological examinations and the number (percentage) of patients with new-onset clinically significant abnormal neurological examinations are to be summarized by visit based on the SAF. Listings are to be provided with flags indicating the abnormal values.

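### The ECG shift table in SAP 5.8.4 cuts a three-level status to normal versus abnormal, so no by-arm ECG status summary isolates new clinically significant readings

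*SAP*

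**What the plan says.** SAP 4.5.9 sets out what is collected at each 12-lead ECG. Besides rate and intervals, "ECG status (normal, abnormal not clinical significant or abnormal clinical significant) is also recorded". That is an ordered scale: normal, abnormal not clinically significant (NCS below), abnormal clinically significant (CS below).

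SAP 5.8.4 sets out what is tabulated. Rate and intervals get descriptive summaries, and "PCSV summary of ECG parameters is to be provided for treatment period, Follow-up period, and overall, for the SAF". For the overall reading, "ECG status (ie, normal, abnormal) is to be reported", followed by "Shift tables are to be provided to present the post-baseline status according to the baseline status (normal or missing / abnormal) by treatment". The section closes with "Listings are to be provided with flags indicating the abnormal values".

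The neurological examination is graded on the same three levels (SAP 4.5.11), but its analysis keeps the clinical distinction: "New-onset clinically significant abnormal neurological examinations and the number (percentage) of patients with new-onset clinically significant abnormal neurological examinations are to be summarized" by visit (SAP 5.8.7).

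**The concern.** The SAP says it collects a judgement of clinical significance on each ECG and then plans no table that uses it. A shift table exists to show who got worse. With abnormal as a single category, a patient with an incidental abnormality at baseline cannot get worse in the table, and in a patient normal at baseline a trivial new finding counts the same as a clinically significant one.

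At stake is how well one safety display can be read. A clinical reader wants to know how many patients in each arm developed a clinically significant ECG. As worded, the status summaries in SAP 5.8.4 do not give that number, although SAP 5.8.7 gives its counterpart for the neurological examination and no reason is stated for the difference.

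**Working it through.** The plan gives no ECG figure to reproduce, and no sample size, power or alpha calculation bears on the point. The check maps each recorded transition to the cell where it would appear.

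**Inputs.** Recorded levels: three (SAP 4.5.9). Reported levels: two (SAP 5.8.4). Baseline rows of the shift table: two, with missing placed alongside normal (SAP 5.8.4). The shift-table sentence gives levels for baseline only. The sentence before it gives two levels for ECG status generally, and the natural reading applies those after baseline as well. Both readings are shown.

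| Recorded shift | Direction | Two levels throughout | Only baseline cut to two |
|---|---|---|---|
| normal → NCS | worse | normal → abnormal | normal → NCS |
| normal → CS | worse | normal → abnormal | normal → CS |
| NCS → CS | worse | abnormal → abnormal | abnormal → CS |
| NCS → normal | better | abnormal → normal | abnormal → normal |
| CS → normal | better | abnormal → normal | abnormal → normal |
| CS → NCS | better | abnormal → abnormal | abnormal → NCS |
| NCS → NCS | same | abnormal → abnormal | abnormal → NCS |
| CS → CS | same | abnormal → abnormal | abnormal → CS |

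The ninth cell, normal → normal, is unaffected.

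**Natural reading.** The 3 × 3 = 9 recorded cells become 2 × 2 = 4.
- Of the 6 recorded changes, 2 (NCS → CS and CS → NCS) move to the diagonal and read as unchanged.
- Of the 3 worsening shifts, 1 (NCS → CS) reads as unchanged. The other 2 share one cell.
- New-onset CS is the sum of normal → CS and NCS → CS. Neither part can be read off, so the total cannot either.

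**Generous reading.** There are 2 × 3 = 6 cells. Normal → CS becomes visible, but NCS → CS shares a cell with CS → CS, a patient who was clinically significant all along. New-onset CS still cannot be counted.

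**Do other outputs supply the count?**
- *PCSV rows (SAP Appendix 11.2).* The ECG rows cover ventricular rate, PR/PQ, QRS and QTcF. They use numeric thresholds and take no account of the CS judgement. A CS reading with every value inside the thresholds enters no row.
- *Adverse events.* Under SAP 4.5.1, "Laboratory results, vital signs, or ECG abnormalities are to be recorded as AEs if they are medically relevant", which it spells out as symptoms, need for treatment, stopping treatment or seriousness. Protocol 9.4.5 has similar criteria and adds further diagnostic testing. A CS rating is not itself a listed trigger. Events that do qualify are tabulated by arm under SAP 5.8.1 by system organ class and preferred term, not by baseline ECG status.
- *Listings.* They flag abnormal values. No CS flag is named, and a listing gives no by-arm count.

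The uncovered remainder is therefore narrow: CS readings inside the PCSV thresholds that also meet no adverse event criterion.

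**The case against.** The case for leaving the table alone has substance.

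- **The post-baseline levels are not stated in the shift-table sentence.** That is true, and the hidden NCS → CS shift rests on the natural reading. The generous reading recovers one of the two parts of new-onset CS but not the total. At the least the sentence needs clarifying.
- **Important worsening is largely caught elsewhere.** This stands in good part. An adverse event includes worsening of an existing condition, and treatment-emergent events are tabulated by arm. A reader might infer that serious ECG deterioration would go unseen. The documents do not support that.
- **Conduction and rate are already covered.** This stands too. A reader might take the status table as the only by-arm view of conduction, but the PCSV rows include PR/PQ, QRS and ventricular rate.
- **ECG is not a flagged risk.** A reader might link the gap to the sympathetic blockade risk in Protocol 3.2.1. That text ties the risk to blood pressure, and ECG is not in its list of precautionary monitoring. No events of special interest are defined.
- **Pooling missing with normal is a convention.** SAP 6.3 groups patients the same way for PCSVs, so it is not a separate ECG error. Showing missing separately is a convenience.
- **Materiality is small.** Scheduled post-baseline ECGs fall only at weeks 1 and 12, plus early termination. The protocol requires no ECG shift table. SAP 1.2.4.2 reports no new safety concern at the week-12 review, drops the laboratory shift tables and plans an abbreviated report. The ECG shift table was nonetheless kept, and a table that is produced should show what was recorded.

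A reader might also want to express the loss as lost power to detect a drug effect on ECGs. The documents give no ECG event rates and plan no ECG test, so any such figure would only reflect the rates assumed.

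**Conclusion.** The point holds as a loss of information in one descriptive safety table. Two of six recorded status changes would read as no change, the two worsening shifts from normal would be merged, and under either reading no by-arm status summary gives the number of patients with a new clinically significant ECG. PCSV and adverse event tables narrow the gap without closing it.

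No hypothesis test, efficacy conclusion or stated figure is affected. How many patients fall in the uncovered remainder cannot be judged from the documents and may be few.

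The conclusion assumes that the three-level status is in the database. That rests on SAP 4.5.9 alone, since Protocol 8.2.3.4 lists only rate and intervals for the case report form. This is a free improvement of low severity.

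**What to change.** In SAP 5.8.4, report ECG status at the three recorded levels and define the shift table by treatment as baseline (normal, NCS, CS, missing) against worst post-baseline status (normal, NCS, CS). Add the number and percentage of patients in each treatment group with a new-onset clinically significant ECG, as SAP 5.8.7 does for the neurological examination.

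If the database holds only two levels, correct SAP 4.5.9 instead so that the two sections agree.

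The cost is a sentence of SAP text and one table shell, using status data that the SAP says are recorded. The table becomes slightly larger. Because SAP Version 2.0 follows the unblinded week-12 review, the revision should be labelled as made after that review. No study procedure changes.

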#### **5.8.5. Physical Exams**

N/A

#### **5.8.6. Joint Pain Questionnaire**

The number (percentage) of patients with worse joint pain are to be summarized by visit and joint (index, non-index) based on the SAF, as well as presented in a listing.

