#### **8.2.3.7. Joint Pain Questionnaire**

A joint pain questionnaire will be completed by the patient at the time points indicated in [Table 1](#). For each knee, hip, and shoulder joint, the patient will be prompted to indicate if he or she has experienced pain. A patient report of having experienced pain will serve as a tool to prompt further evaluations as deemed necessary by the investigator.

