## 2. INVESTIGATION PLAN

### 2.1. Study Design and Randomization

This is a multicenter, Phase 2, multicenter, randomized, double-blind, multi-dose, parallel-arm, placebo-controlled study designed to evaluate the safety and efficacy of REGN5069 in patients with pain due to osteoarthritis of the knee. Up to approximately 240 patients are randomized in a 1:1:1 ratio to receive a low dose of REGN5069 at 100 mg IV Q4W, a high dose of REGN5069 at 1000 mg IV Q4W, or matching placebo Q4W, for a total of 3 doses Q4W during the 12-week treatment period.

Randomization is stratified by Kellgren-Lawrence (K-L) category (2-3 vs 4) of the index knee joint at the screening visit and participation in the Moticon sub-study (yes vs no). The use of the stratification factor based on participation in the Moticon sub-study ensures balance in the treatment assignments within the Moticon sub-study. The index knee joint is defined as the knee joint affected by OA and selected for primary assessment for this study.

An independent Data Monitoring Committee (IDMC) is monitoring unblinded data. Based on these reviews in the context of the totality of evidence, if there are significant concerns at any time regarding a safety issue, the IDMC may make a recommendation to the sponsor to temporarily pause, alter, or terminate the study. Once recommendations from the IDMC have been received, further discussions may be conducted, if appropriate, and the sponsor is to determine if these or other actions should be taken.

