#### **4.5.12. Other Safety Variables**

- Joint Pain Questionnaire: A joint pain questionnaire is to be completed by the patient at the time points indicated in the Schedule of Events in [Table 3](#). For each knee, hip, and shoulder joint, the patient is prompted to indicate if he or she has experienced worse pain. Assessments include:
  - Patients with significantly worse joint pain in any joint at each scheduled visit
  - Patients with significantly worse joint pain by joint at each scheduled visit
- Joint replacement: an end-of-study phone call was to be conducted at approximately 52 weeks after the first dose of study drug. The purpose of the end-of-study phone call was to determine whether a patient underwent, is scheduled for, or is on a waiting list to receive joint replacement surgery, or whether joint replacement was recommended but the patient elected to defer since his/her last in-clinic visit. Patients were to also be asked to submit pre-operative imaging (X-ray and MRI, if available) for adjudication and to provide joint material for histological and molecular analyzes, if feasible. Assessments included:
  - Patients with joint replacement (all joint replacements)
  - Reason for joint replacement (all joint replacements)
  - Time to joint replacement (all joint replacements)
- Knee society score for joint replacement: an investigator-completed questionnaire that is used to objectively measure a patient's ability to function before and after total knee arthroplasty

As the study will now end when the last patient completes the week 36 visit, the week 52 phone call will not be performed for most of the patients; all available Joint Replacement information will be summarized in a listing.

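### SAP 5.8.6 does not carry through the by-joint and any-joint pain questionnaire summaries defined in SAP 4.5.12; its index/non-index split pools five of the six joints.

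*SAP*

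**What the plan says.** Protocol 8.2.3.7 describes the instrument: "For each knee, hip, and shoulder joint, the patient will be prompted to indicate if he or she has experienced pain". SAP 4.5.12 repeats this with a different question: "For each knee, hip, and shoulder joint, the patient is prompted to indicate if he or she has experienced worse pain". Both cover six joints.

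SAP 4.5.12 then lists two assessments: "Patients with significantly worse joint pain in any joint at each scheduled visit" and "Patients with significantly worse joint pain by joint at each scheduled visit".

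The analysis is planned in SAP 5.8.6. Counts and percentages of patients with worse joint pain "are to be summarized by visit and joint (index, non-index) based on the SAF", and the same sentence adds a patient listing. SAP 5.8 provides that safety summaries are shown for each treatment group. No other SAP section plans a summary of this questionnaire.

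The index joint is a knee by definition (SAP 2.1): "The index knee joint is defined as the knee joint affected by OA and selected for primary assessment for this study".

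**The concern.** The variable section asks for results by joint and for any joint. The analysis section delivers two classes, and one of them mixes the other knee with both hips and both shoulders. In a knee OA population the other knee may well contribute most of the reports in that class, although the documents give no rates. A difference between arms in hips or shoulders would then be spread over a larger background.

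Protocol 3.2.1 names the questionnaire among the precautionary measures adopted because of the arthropathies seen with anti-NGF agents. Other scheduled data on hips and shoulders are limited. Under the protocol's schedule of events (Table 1), these joints have radiographs at screening and week 36. The week 12 film and all scheduled MRIs cover the index knee only. At the phone calls at weeks 20, 28 and 32, the questionnaire is the only scheduled joint-specific instrument. Joint examinations take place at clinic visits, but SAP 4.5.10 and 5.8.5 define no variable or analysis for them, so a finding reaches the tables only if it is entered as an adverse event.

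**Working it through.** **Text comparison**

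| Item | SAP 4.5.12 | SAP 5.8.6 |
|---|---|---|
| Joints asked about | 6 (two knees, two hips, two shoulders) | not restated |
| By-joint summary | yes, each visit | two classes, index and non-index |
| Any-joint summary | yes, each visit | not mentioned |
| Term used | *significantly worse* | *worse* |
| Patient listing | not mentioned | yes |

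The index joint is one knee, so the non-index class holds 6 − 1 = 5 joints.

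**The plan's own figure.** The documents give no rate, effect size or test for this questionnaire. Their only power figure is for the primary endpoint: about 80% with 80 per group, SD 2.3, difference 1.1 and 15% dropout. It reproduces: 80 × 0.85 = 68 evaluable per group gives 79.1% by the noncentral t. It does not bear on this point, which borrows only the 80 per arm.

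**Illustration of dilution.** All rates below are assumptions. Let h be the rate of worse pain in either hip, s in either shoulder and k in the other knee, with joints independent and s and k equal in both arms. Then

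pooled rate = 1 − (1 − k)(1 − h)(1 − s).

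With h = 0.05 on placebo and 0.20 on drug, the pooled difference is 0.15 × (1 − k)(1 − s). Power is for a two-sided Fisher exact test at 0.05 with 80 per arm.

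| Other knee k | Shoulder s | Placebo | Drug | Difference | Power |
|---|---|---|---|---|---|
| separate hip row | – | 5.0% | 20.0% | 15.0 points | 0.79 |
| 5% | 2% | 11.6% | 25.5% | 14.0 points | 0.56 |
| 10% | 5% | 18.8% | 31.6% | 12.8 points | 0.40 |
| 20% | 10% | 31.6% | 42.4% | 10.8 points | 0.24 |
| 30% | 10% | 40.2% | 49.6% | 9.5 points | 0.17 |
| 40% | 10% | 48.7% | 56.8% | 8.1 points | 0.13 |

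For example, k = 20% and s = 10% give 1 − 0.80 × 0.95 × 0.90 = 0.316 on placebo and 1 − 0.80 × 0.80 × 0.90 = 0.424 on drug.

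At 68 per arm, allowing for the planned dropout, the separate hip row itself has power of about 0.70.

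**A second set of assumptions.** Take hip and shoulder pain combined at 5% against 15%, a ratio of 3.0. Pooled with other-knee pain of 10%, this becomes 14.5% against 23.5% (ratio 1.6). With other-knee pain of 50%, it becomes 52.5% against 57.5% (ratio 1.1). The direction is the same and the size again depends on the background.

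**The case against.** A reader might infer that the SAP hides a hip or shoulder signal, or that it deliberately dropped those joints. The documents do not support either reading.

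- SAP 5.8.6 also plans a listing, so joint-level responses stay available. This stands. A listing is not a comparison by arm, however.
- SAP 4.5.12 still contains the by-joint and any-joint assessments. The fault is an incomplete carry-over between two sections, with no stated decision behind it. This stands.
- The protocol gives the questionnaire a role in the individual patient: "A patient report of having experienced pain will serve as a tool to prompt further evaluations as deemed necessary by the investigator". That role does not depend on table rows. Joint harm is also captured elsewhere. Adverse events are tabulated by preferred term and arm (SAP 5.8.1), adjudicated arthropathy is summarized by arm (SAP 5.8.8), joint examinations are done at clinic visits, and radiographs are to be considered for worsening joint pain. This stands and limits the consequence. It does not reconcile the two sections.
- The low power values come from high assumed backgrounds. The table counts worse pain, which may be less common than pain, and with low backgrounds pooled power is 0.40 to 0.56. Independence is assumed too, and no test between arms is planned. This stands. The figures serve only as a measure of lost visibility and must be shown over their whole range.
- The index/non-index label could be meant for the two knees inside a by-joint table. That is possible but is not what 5.8.6 says. If it labelled the knees alone, hips and shoulders would have no summary row at all. The wording needs correcting on any of these readings.
- SAP Version 2.0 was written after the week 12 results, with the indication discontinued, an abbreviated report planned and one joint replacement recorded (SAP 1.2.4.2). This stands and keeps the priority low.

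**Conclusion.** The inconsistency is real and minor. SAP 5.8.6, read literally, gives two joint classes where SAP 4.5.12 specifies each joint and any joint, and five of the six joints share one row. A hip or shoulder imbalance would be diluted in the by-arm questionnaire table and, within the questionnaire data, separable only in the listing.

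The size cannot be fixed from the documents. For an assumed hip difference of 5% against 20% with 80 per arm, illustrative power goes from about 0.79 in its own row to between 0.56 and 0.13 pooled. This rests on assumed backgrounds of 5% to 40% in the other knee and 2% to 10% in the shoulders, and on independent joints. The summary is descriptive, so these values do not describe the failure of a planned test. The point does not extend to the study's overall ability to detect joint harm, because the adverse-event and adjudicated-imaging tables are unaffected.

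**What to change.** In SAP 5.8.6, replace the index/non-index split with a summary by visit and treatment group for each joint as in SAP 4.5.12 (index knee, other knee, hips, shoulders), plus a row for any joint. SAP 4.5.12 does not say that left and right are combined. If the sides are pooled for hips or shoulders, say so in both sections.

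Use one term, *worse* or *significantly worse*, in 4.5.12 and 5.8.6, and tie it to the question on the form; Protocol 8.2.3.7 speaks only of pain. Keep the listing.

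The cost is a sentence of SAP text and a few table rows: seven per visit (six joints plus any joint) against two now, or fewer if sides are combined. The questionnaire is already answered for each joint, so no change to design or data collection is needed.
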